1.1.3.4 Gliomas

The incidence of primary brain tumors in the United States (US) is about 17,000 per year, with a case fatality of about 10,000 per year. Gliomas account for up to 80% of primary brain tumors and they account for significant mortality. Gliomas can be classified as either high-grade (or malignant), or low-grade. The low-grade gliomas (LGG) themselves are a diverse group of glial tumors with an annual incidence in the US is about 1800 cases (*CBTRUS: Statistical Report 2002*). Histologic subtypes of LGG include diffuse astrocytomas (WHO grade II astrocytomas), oligodendroglomas and mixed oligoastrocytomas (Ashby et al. 2004). The majority of these tumors are of mixed histology.

Despite medical management with surgery and irradiation the median 10-year survival rates for LGG range from 17-49%. Survival is limited by recurrence and progression of LGG to high-grade gliomas. Factors influencing survival in these patients include histologic subtype, age, extent of surgical resection, and presence of 1p 19q status (Pignatti et al 2002; Yeh et al. 2005; Smith et al. 2000). One particular subtype of LGG, the pilocytic astrocytomas, usually occurs in the cerebellum of children. These tumors are often completely resectable and are associated with a 10-year survival of >80%. For the purposes of this project only supratentorial non-pilocytic LGG in adults will be considered.

The management of patients with residual low grade glioma following surgical resection is not standardized (Lang et al. 2006). Options include surveillance scans and treatment at the time of tumor progression, versus the use of radiation therapy soon after the surgical procedure. Adjuvant chemotherapy following radiation is not considered a standard approach (Grier and Batchelor, 2003).

Low grade gliomas are diffuse in nature and the treatment fields for radiation therapy can be large. The potential complications of radiation therapy to the brain include seizures, cognitive decline, endocrinopathies, necrosis and vasculopathies. In addition, any of a number of secondary malignancies may arise after radiation treatment including meningiomas, gliomas and sarcomas. Given the potential for long term survival of patients with LGG and the morbidity associated with radiation therapy, alternative approaches in this setting are appealing and are being evaluated (Grier and Batchelor, 2003).

In an effort to reduce the use of radiotherapy, several studies have evaluated the use of chemotherapy as initial treatment of LGG. Tumor regressions using a combination of procarbazine, lomustine and vincristine in patients with an oligodendroglial component has been demonstrated (Buckner et al. 2003; Stege et al. 2005). More recently, temozolomide showed activity as treatment for recurrent LGG. However, the role of chemotherapy as up-front treatment of LGG continues to be evaluated (Grier and Batchelor, 2003; Hoang-Xaun et al. 2004; Brada et al. 2003).

The role of chemotherapy in adult patients with recurrent LGG has also not been extensively investigated (Quinn et al. 2003; Pace et al. 2003; Soffietti et al. 1998). Nitrosourea based chemotherapy and temozolomide have both been evaluated. In small studies, temozolomide

appears to have response rates ranging from 47-61% and 1 year progression free survival from 39-76% (Quinn et al. 2003; Pace et al. 2003). Although these numbers appear promising for the treatment of recurrent LGG with chemotherapy, other treatment strategies are needed for this patient population, especially in the setting of progression to malignant glioma. With a better understanding of the signaling pathways important for tumor growth and invasion, novel targeted therapies are being evaluated.

1.1.3.5 PTEN methylation and PKB/Akt phosphorylation in gliomas

Alterations in the tumor suppressor protein PTEN are common in gliomas and result in activation of the PI3K pathway, as evidenced by phosphorylation of PKB / Akt. Whereas mutation of PTEN is common in *de novo* malignant gliomas (Choe et al. 2003; Rasheed et al. 1997; Ermoian et al. 2002), methylation of the PTEN promoter is thought to be the underlying mechanism of PTEN alteration found in low-grade gliomas and secondary malignant gliomas (Wiencke et al. 2007).

In fact, methylation of the PTEN promoter occurs frequently in low-grade gliomas. Whereas there is no evidence of PTEN promoter methylation in normal brain and only 9% methylation in *de novo* glioblastomas, low-grade tumors displayed methylation of PTEN promoter in 43-67% of low-grade glioma cases, and in 68-82% of secondary high grade glioma cases. The differences in PTEN promoter methylation frequencies for low-grade gliomas were highly statistically significant ($P<0.001$) (Wiencke et al 2007).

Not only is methylation of the PTEN promoter frequent and associated specifically with low-grade gliomas and secondary malignant gliomas, there is evidence that PTEN methylation also leads to functional activation of the PI3K pathway, which is thought to be important for tumor transformation and growth (Wiencke et al. 2007). Furthermore, a retrospective study of 43 LGG (grade II) tumor specimens from newly diagnosed patients show a trend towards decreased overall survival in low grade glioma patients with PTEN promoter methylation compared to those without methylation (McBride et al. 2007).

Because of the clinical significance of PTEN promoter methylation and its effects on the PI3K pathway, therapies that target tumors with PI3K activity may be of clinical benefit in low-grade gliomas. The mammalian target of rapamycin (mTOR) is downstream to the (PI3K) / PTEN-AKT survival pathway and is therefore an ideal target for low-grade glioma and secondary malignant glioma patients with PTEN promoter methylation (Choe et al. 2003; Xu et al. 2004; Neshat et al. 2001). In fact, there is evidence that tumors expressing activated PKB/Akt appear particularly sensitive to mTOR inhibition (Gera et al. 2004; Noh et al. 2004).

1.1.3.6 Clinical experience with mTOR inhibitors for gliomas

There is extensive clinical experience with mTOR inhibitors including the evaluation in the treatment of patients with malignant glioma (Reardon et al. 2006). Perhaps most exciting are recent studies in which patients with Tuberous Sclerosis Complex (TSC) and low-grade

gliomas were treated with an mTOR inhibitor (rapamycin most commonly), resulting in tumor regression in every treated patient. In one patient treatment was interrupted, resulting in tumor re-growth, followed by further regression when treatment with the mTOR inhibitor resumed (Franz et al. 2006). The success of this approach adds credence to our plan to treat low-grade gliomas with RAD001 because of the genetic underpinnings of low-grade gliomas in TSC patients. In brief, mutations in either hamartin or tuberin, the tuberous sclerosis gene products, result in elevated mTOR signaling. As a result, afflicted individuals develop hamartomatous growths in multiple organs, and 5-15% of TSC patients develop low-grade central nervous system neoplasms in the form of subependymal giant cell astrocytomas (SEGAs). Although SEGAs rarely respond to radiation or chemotherapy, striking tumor regressions were documented after treatment with mTOR inhibitor in these TSC patients.

1.4 Rationale

We have shown that methylation of the PTEN promoter occurs frequently in low-grade gliomas and secondary glioblastomas, and is associated with PI3K signaling and PKB/Akt phosphorylation (Wiencke et al. 2007). Given these findings, and the link between (mTOR) and the (PI3K) / PTEN-AKT survival pathway, we hope that RAD001 will also prove efficacious in the treatment of low-grade gliomas and secondary malignant gliomas as delineated in the study proposed herein.

In this study, molecular features, including PTEN status and PKB/Akt phosphorylation will be assessed prospectively in this trial to test the hypothesis that those tumors with PTEN methylation and consequent PKB/Akt phosphorylation will preferentially respond to mTOR inhibition.

1.5 Rationale for additional radiographic imaging as an exploratory aim

Standard anatomic MRI in conjunction with clinical evaluation such as neurologic status and corticosteroid use, remains the key determinant of response to therapy and the evaluation of tumor recurrence for LGG (Just and Thelen 1988; Dean et al. 1990; Ginsberg et al. 1996). Increase in contrast enhancement, worsening cerebral edema, and mass effect are universal traits of malignant transformation. Acquiring tissue samples to confirm tumor upgrade, although considered the “gold standard” for determining the presence of viable tumor, can result in both false positives and negatives that relate to sampling error (Earnest et al. 1988; Kleihues et al. 1993). Recent studies using MR spectroscopic imaging (MRSI) suggest that *in vivo* levels of metabolites such as choline, creatine, N-acetylaspartate, lactate and lipids provide more-reliable measures of the presence of recurrent tumor. Perfusion-weighted imaging (PWI) and diffusion-weighted imaging (DWI) have been explored for patients with newly diagnosed glioma, but only on a limited basis for patients with recurrent LGG. Techniques to characterize the molecular morphology of pre-specified areas in addition to neuroimaging parameters may better define the biologic behavior of such lesions.

Many of the newer drugs being studied in neuro-oncology target specific aberrant pathways and are cytostatic rather than cytotoxic. Examples include anti-invasive and anti-angiogenic

agents. These agents may cause stability of the tumor rather than regression, and surrogate biomarkers are important in the assessment of these types of agents. Pending funding availability, we will prospectively incorporate metabolic and physiologic imaging to this trial to allow us to assess the ability of the key parameters to predict clinically relevant endpoints such as treatment related radiographic response, time to progression and survival.

2 Study objectives

Primary

To determine progression-free survival at 6 months associated with use of RAD001 in patients initially diagnosed with low-grade glioma who undergo biopsy or subtotal resection at the time of recurrence with pathologic evidence of recurrent low-grade glioma.

Secondary

1. To further delineate the safety profile of RAD001 in patients with recurrent LLG.
2. To assess overall survival (OS) in patients treated with RAD001.
3. To assess the Objective Response rate (ORR) in patients treated with RAD001.
4. To assess the correlation of phosphorylated PKB/Akt and PTEN expression with response, progression status by 6 months, and OS in patients treated with RAD001.

Exploratory

1. To determine progression-free survival at 6 months associated with use of RAD001 in patients initially diagnosed with low-grade glioma who have already received radiotherapy, and who undergo biopsy or subtotal resection at the time of recurrence with pathologic evidence of high-grade glioma.
2. Pending adequate funding, to assess the ability of metabolic and physiologic imaging parameters such as MR spectroscopy, perfusion-weighted imaging, and diffusion-weighted imaging to predict clinically-relevant endpoints such as time to progression and survival.

3 Investigational plan

3.1 Overall study design

A single-arm, one-stage phase II trial of RAD001 will be undertaken. Sixty patients will be enrolled. The target population will be patients with a diagnosis of low-grade glioma who experience a recurrence and who undergo a biopsy or subtotal resection at the time of recurrence with pathologic evidence of recurrent glioma. The purpose of this study is to accrue patients to evaluate a pharmacologic agent.

3.2 Study population

3.2.1 Patient population

It is anticipated that most low-grade glioma patients completing surgical resection for recurrence will be eligible for enrollment and will choose to participate. Based on current patient volume in the UCSF neurologic-oncology clinic, it is expected that a minimum of 3 patients per month will be enrolled. Therefore, accrual can be completed in a 20 month period. Patients will be recruited with no preference to gender. Minorities will actively be recruited to participate. In order to evaluate our primary objective, enrollment will continue until at least 40 low-grade glioma patients have enrolled.

3.2.2 Inclusion and exclusion criteria

Patients must have baseline evaluations performed prior to the first dose of study drug and must meet all inclusion and exclusion criteria. Results of all baseline evaluations, which assure that all inclusion and exclusion criteria have been satisfied, must be reviewed by the Principal Investigator or his/her designee prior to enrollment of that patient. In addition, the patient must be thoroughly informed about all aspects of the study, including the study visit schedule and required evaluations and all regulatory requirements for informed consent. The written informed consent must be obtained from the patient prior to enrollment. The following criteria apply to all patients enrolled onto the study unless otherwise specified.

3.2.2.1 Baseline Characteristics Inclusion criteria

- Patients must have a Karnofsky performance status of ≥ 60
- Patients must have a life expectancy > 8 weeks
- Patients must be ≥ 18 years old
- All patients must sign an informed consent document indicating that they are aware of the investigational nature of this study
- Patients must sign an authorization for the release of their protected health information
- Patients must have an MRI scan performed within 14 days prior to initial protocol treatment
- Patients must be registered in the UCSF Neuro-Oncology database prior to treatment with study drug
- Adequate bone marrow function as shown by: ANC $\geq 1.5 \times 10^9/L$, Platelets $\geq 100 \times 10^9/L$, Hb >9 g/dL
- Adequate liver function as shown by:
 - serum bilirubin $\leq 1.5 \times$ ULN
 - INR < 1.5 (Anticoagulation is allowed if target INR ≤ 1.5 on a stable dose of warfarin or on a stable dose of LMW heparin for > 2 weeks at the time of registration)
 - ALT and AST $\leq 2.5 \times$ ULN

- Adequate renal function: serum creatinine $\leq 1.5 \times$ ULN
- Fasting serum cholesterol $\leq 300 \text{ mg/dL}$ OR $\leq 7.75 \text{ mmol/L}$ AND fasting triglycerides $\leq 2.5 \times$ ULN. NOTE: In case one or both of these thresholds are exceeded, the patient can only be included after initiation of appropriate lipid lowering medication.

3.2.2.2 Histologic Inclusion Criteria

- Patients must have histologically proven intracranial low-grade glioma at initial diagnosis. Low-grade gliomas include: astrocytoma, oligodendrogloma and mixed oligoastrocytoma. Pilocytic astrocytomas are excluded
- Patients must have unequivocal evidence for tumor recurrence or progression by histology as determined by review of pathology by an attending neuro-pathologist at UCSF
- If most recent histology shows progression to high grade glioma, patients must have had prior radiotherapy in order to be eligible
- Paraffin-embedded sections of tissue acquired from surgery at the time of suspected recurrence must be available for analysis

3.2.2.3 Radiographic Inclusion Criteria

- Patients must have evidence for tumor recurrence or progression by MRI as determined by radiographic review of images by an attending neuro-oncologist or neuro-radiologist at UCSF
- If the steroid dose is increased between the date of the MRI and registration on the trial, a new baseline MRI is required. This MRI must be performed after ≥ 5 days on a stable or decreasing dose of steroids
- An MRI must be used throughout the period of protocol treatment for tumor measurement
- Patients must have evaluable disease

3.2.2.4 Prior Therapy Inclusion Criteria

- Patients may have had treatment (including radiotherapy) for any number of relapses prior to this recurrence
- Patients must be at least 4 weeks from the completion of any radiation therapy
- Patients must be less than 4 months from the surgical procedure for this recurrence
- Patients must have recovered from the toxic effects of prior therapy:
 1. 4 weeks from any investigational agent.
 2. 4 weeks from prior cytotoxic therapy (except 6 weeks from nitrosoureas, 3 weeks from procarbazine, 3 weeks from vincristine)

3. 3 weeks for non-cytotoxic or biologic agents e.g., interferon, tamoxifen, thalidomide, cis-retinoic acid, tarceva, etc. Note a 3-week washout is required for prior treatment with Bevacizumab

3.2.2.5 Exclusion criteria

- Patients, who have not recovered from the side effects of a major surgery or significant traumatic injury or patients that may require major surgery during the course of the study
- Patients receiving chronic, systemic treatment with corticosteroids or another immunosuppressive agent. Topical or inhaled corticosteroids, and treatment with low dose Decadron (≤ 3 mg daily) are allowed.
- Other than surgery, patients may not have therapy for this recurrence (including radiation). Supportive care such as steroids or anti-epileptics does not constitute treatment of recurrence
- Patients must not have any significant medical illnesses that in the investigator's opinion cannot be adequately controlled with appropriate therapy or would compromise the patient's ability to tolerate this therapy.
- Patients with a history of any other cancer (except for adequately treated carcinoma of the cervix or basal or squamous cell carcinomas of the skin), unless in complete remission and off of all therapy for that disease for a minimum of 3 years are ineligible.
- Patients should not receive immunization with attenuated live vaccines within one week of study entry or during study period. Close contact with those who have received attenuated live vaccines should be avoided during treatment with everolimus. Examples of live vaccines include intranasal influenza, measles, mumps, rubella, oral polio, BCG, yellow fever, varicella and TY21a typhoid vaccines.
- Uncontrolled brain or all leptomeningeal metastases, including patients who continue to require glucocorticoids for brain or leptomeningeal metastases
- Patients who have any severe and/or uncontrolled medical conditions or other conditions that could affect their participation in the study such as:
 - Symptomatic congestive heart failure of New York heart Association Class III or IV
 - unstable angina pectoris, symptomatic congestive heart failure, myocardial infarction within 6 months of start of study drug, serious uncontrolled cardiac arrhythmia or any other clinically significant cardiac disease
 - severely impaired lung function
 - uncontrolled diabetes as defined by fasting serum glucose $>1.5 \times$ ULN (Note: Optimal glycemic control should be achieved before starting trial therapy.)
 - active (acute or chronic) or uncontrolled severe infections
 - liver disease such as cirrhosis or severe hepatic impairment (Child-Pugh class C).

- A Hepatitis B/C blood test must be done at screening for all patients. Patients who test positive for Hepatitis C antibodies and the Hepatitis B antigen are ineligible
- A known history of HIV seropositivity
- Impairment of gastrointestinal function or gastrointestinal disease that may significantly alter the absorption of RAD001 (e.g., ulcerative disease, uncontrolled nausea, vomiting, diarrhea, malabsorption syndrome or small bowel resection)
- Impaired lung function: O₂ saturation 88% or less at rest on room air by Pulse Oximetry. If O₂ saturation is ≤ 88% at rest, further pulmonary function tests (PFTs) should be ordered to confirm normal pulmonary function and eligibility.
- Patients with an active, bleeding diathesis
- Female patients who are pregnant or breast feeding, or adults of reproductive potential who are not using effective birth control methods. Adequate contraception must be used throughout the trial and for 8 weeks after the last dose of study drug, by both sexes. (Women of childbearing potential must have a negative urine or serum pregnancy test within 7 days prior to administration of RAD001)
- Male patient whose sexual partner(s) are WOCBP who are not willing to use adequate contraception, during the study and for 8 weeks after the end of treatment
- Patients who have received prior treatment with an mTOR inhibitor (e.g., sirolimus, temsirolimus, everolimus).
- Patients with a known hypersensitivity to RAD001 (everolimus) or other rapamycins (e.g., sirolimus, temsirolimus) or to its excipients
- History of noncompliance to medical regimens
- Patients unwilling to or unable to comply with the protocol

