Reactivation/flare of Hepatitis B (HBV) has been observed in patients with cancer receiving chemotherapy (Yeo 2004). Sporadic cases of Hepatitis B reactivation have also been seen in
Protocol: RAD001

Version 7.0 03/15/2011

this setting with everolimus. Use of antivirals during anti-cancer therapy has been shown to reduce the risk of Hepatitis B virus reactivation and associated morbidity and mortality (Loomba 2008). A detailed assessment of Hepatitis B/C medical history must be done for all patients at screening, with testing performed prior to the first dose of everolimus.

Hypersensitivity reactions manifested by symptoms including, but not limited to, anaphylaxis, dyspnea, flushing, chest pain or angioedema (e.g. swelling of the airways or tongue, with or without respiratory impairment) have been observed with everolimus.

Hyperglycemia has been reported in clinical trials. Monitoring of fasting serum glucose is recommended prior to the start of everolimus therapy and periodically thereafter. Optimal glycemic control should be achieved before starting a patient on everolimus. Mouth ulcers, stomatitis and oral mucositis have been seen in patients treated with everolimus. In such cases topical treatments are recommended, but alcohol- or peroxide-containing are not allowed.

Elevations of serum creatinine, usually mild, have been reported in clinical trials. Monitoring of renal function, including measurement of blood urea nitrogen (BUN) or serum creatinine, is recommended prior to the start of everolimus therapy and periodically thereafter.

Decreased hemoglobin, lymphocytes, platelets and neutrophils have been reported in clinical trials. Monitoring of complete blood count is recommended prior to the start of everolimus therapy and periodically thereafter.

Everolimus is not recommended in patients with severe hepatic impairment, (Child-Pugh class C).

The use of live vaccines and close contact with those who have received live vaccines should be avoided during treatment with everolimus.

Hypophosphatemia, hypomagnesemia, hyponatremia and hypocalcemia have been reported as serious adverse reactions. Electrolytes should be monitored in patients treated with RAD001.

Table 3-1 provides general recommendations for the management of patients, with suspected drug toxicities while on treatment with RAD001 as single-agent therapy.

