3.2.5.3 Management of Hepatitis B reactivation

If any patients experience reactivation of hepatitis B during treatment, the patient will be removed from study protocol and referred to the appropriate specialist for management of Hepatitis B.

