3.4 Visit schedule and assessments

3.4.1 Visit schedule

3.4.1.1 Screening Assessments

Written informed consent must be obtained and documented in the medical record before starting protocol therapy. After receiving a subject's agreement to participate in the study and verifying that the subject eligibility criteria, the study site will begin further pretreatment evaluation as follows:

- Clinical Evaluation: A complete history and neurological examination (including clinical assessment of Karnofsky Performance Status, Neurological function, neurologic exam score, Vital signs, Physical, and Mental Status) is to be done within 14 days of initial protocol treatment.
- Radiographic Evaluation: An MRI scan must be performed within 14 days prior to initial treatment on a dose of steroids that has been stable or decreasing for 5 days or more. MR spectroscopy are optional.
- Vital Signs: Height, pulse, blood pressure, respiration rate, temperature and weight. Blood pressure, pulse and respiration rate should be measured on patients.
- Laboratory Evaluation: Blood tests may be performed at the UCSF GCRC, at the UCSF Neuro-oncology clinic, or at a local laboratory. Pre-study laboratory tests must be obtained with 14 days prior to initial protocol treatment. Pre-study laboratory tests shall include:
 - CBC, platelets, differential, PT (INR)
 - Sodium, potassium, chloride, bicarbonate, calcium, fasting glucose, albumin, total protein, BUN, serum creatinine
 - T. bilirubin, AST, ALT, alkaline phosphatase, uric acid, phosphorus,
 - Fasting serum lipid profile (total cholesterol, triglycerides, HDL and LDL)
 - serum pregnancy test for women of childbearing potential (performed within 7 days of initial protocol treatment).

- Electrocardiogram (ECG): A standard 12 lead ECG is to be performed within 14 days of initial protocol treatment and significant findings must be recorded.
- Lung function: Pulse Oximetry and Chest X-ray must be performed within 14 days prior to initial protocol treatment

Hepatitis B/C testing: Patients will be tested for the following hepatitis serologic markers: HBsAg, HBs Ab, HBc Ab Total, HBc IgM Ab and HCV antibodies.

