 - Serum pregnancy test: for women of childbearing potential every 2 months for 12 months and then every 3 months while on protocol therapy and 12 weeks after discontinuing protocol therapy.
 - Note the coadministration of RAD001 and oral anticoagulants is possible but should be subject to verification of coagulation (INR) once steady state is reached (after one week's treatment).
- Hepatitis B testing: Patients who test positive for hepatitis B antibodies without receiving prior vaccination will be monitored for HBsAg every 4 weeks.

- Medication Evaluation: All relevant information regarding drug doses, concomitant medications and doses, evaluable lesions with measurements, tumor response, laboratory examinations, and treatment-related toxicities shall be documented in the patient's medical record and flow sheets. Patients will maintain a treatment diary while on therapy. The Treatment Diary will be initiated on Day 1 of therapy and continue throughout treatment. Treatment

Diaries will be collected from the patient at 1 week, and then every 2 months for the first 12 months, then every 3 months until the patient discontinues therapy.

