3.4.1.4 Summary of Assessments

	Initial Screen	1-month Assessment	Assessments every 8 weeks (+3/-7days unless otherwise noted) for year 1 of therapy	Assessments every 12 weeks (+3/-7days unless otherwise noted) after first year of therapy	30 days after completing protocol therapy
Procedure:					
Clinical Evaluation	X		X	X	

Vital Signs	X		X	X	
Neurologic Exam	X		X	X	
Toxicity Check	X	X	X	X	X
Chest X-Ray	X		X Q 8 weeks (+/-7days)	X Q 12 weeks (+/-7days)	
Pulse Oximetry	X		X	X	
ECG	X				
Laboratory/ Diagnostic Tests:					
Serum pregnancy for women of child-bearing potential	X		X Q 8 weeks (+/- 3 days)	X Q 12 weeks (+/- 3 days)	
CBC with diff and platelets					
Chemistries					
Liver function tests					
Fasting cholesterol / triglycerides					
MRI of the brain	X		X	X	
Hepatitis B/C testing HBsAg, HBs Ab, HBc Ab Total, HBc IgM Ab and HCV antibodies	X		Patients who test positive for HBV antibodies without prior vaccination will be tested for HbsAg every 4 weeks (+/- 7 days) for re-activation		
Translational Research:					
Archival tumor tissue	X				
Study Drug:					
RAD001 starting dose:			10mg		

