3.4.7.2 Laboratory evaluations

- *please see section 3.4.1 for schedule for initial assessment and during follow up*

Hematology

Hematology must include hemoglobin, hematocrit, platelets, total white blood cell count (WBC) and differential. PT (INR) evaluation will be included for baseline evaluations.

Blood chemistry

Blood chemistry must include sodium, potassium, chloride, bicarbonate, calcium, glucose, creatinine, blood urea nitrogen, albumin, total protein, SGOT (AST), SGPT (ALT), total bilirubin, alkaline phosphatase, uric acid, phosphorus, serum lipid profile (triglycerides, total cholesterol, HDL and LDL).

Because accurate serum glucose and lipid measurements are required, patients should be fasting at the time of the blood sampling.

Hepatitis B Virus testing

Patients will be tested for the following hepatitis B serologic markers prior to enrolling on the trial: HBsAg, HBs Ab, and HBc Ab Total, and HBc IgM Ab.

HbsAg monitoring should be performed every 4 weeks if a patient tests positive for the hepatitis B antibodies without prior vaccination

Hepatitis C Virus testing

Patients will be tested for HCV Ab prior to enrolling on the trial.

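### As written, the hepatitis exclusion requires both markers to be positive, so an HBsAg-positive, HCV-antibody-negative patient passes serology, and the planned HBsAg monitoring cannot show reactivation in that patient

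*Combined protocol and SAP*

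**What the plan says.** **Eligibility.** Section 3.2.2.5 first requires testing: "A Hepatitis B/C blood test must be done at screening for all patients". The consequence follows: "Patients who test positive for Hepatitis C antibodies and the Hepatitis B antigen are ineligible".

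**Screening panel.** Section 3.4.1.1: "Patients will be tested for the following hepatitis serologic markers: HBsAg, HBs Ab, HBc Ab Total, HBc IgM Ab and HCV antibodies". Section 3.4.7.2 places the hepatitis B and C tests before enrolment. Neither section says which result excludes a patient, and no viral-load test is listed.

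**Monitoring on treatment.** Section 3.4.1.2: "Patients who test positive for hepatitis B antibodies without receiving prior vaccination will be monitored for HBsAg every 4 weeks". Section 3.4.7.2 repeats the rule, and the table in 3.4.1.4 adds the purpose: "Patients who test positive for HBV antibodies without prior vaccination will be tested for HbsAg every 4 weeks (+/- 7 days) for re-activation".

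**Recognised risk and action.** Sections 1.1.3.3 and 3.2.5 list hepatitis B reactivation among the viral infections described with everolimus. Section 3.2.5 also reports sporadic cases in cancer patients on the drug, and says that antivirals given during cancer treatment "reduce the risk of Hepatitis B virus reactivation and associated morbidity and mortality". Section 3.2.5.3 gives the action: "If any patients experience reactivation of hepatitis B during treatment, the patient will be removed from study protocol", with referral to a specialist. It does not define reactivation.

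**The concern.** The exclusion joins two test results with a plain conjunction. Taken at its word, it removes only patients positive on both, which leaves in the patient for whom hepatitis B matters most: HBsAg present, HCV antibody absent.

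The monitoring plan appears to assume that this patient is already out. It starts from hepatitis B antibody and looks for HBsAg as the sign of reactivation, which is informative only in someone who began HBsAg-negative. If the literal wording lets an HBsAg-positive patient in, the only reactivation-specific test in the protocol tells the investigator nothing new. The removal rule in 3.2.5.3 then depends on routine liver tests and symptoms.

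What is at stake is the safety of individual patients on an immunosuppressive drug. The primary analysis, sample size, power and alpha are not touched. The documents state no harm for patients positive only for HCV antibody, and none is claimed here.

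**Working it through.** The plan gives no figure to reproduce on this point. The check has three steps.

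**Step 1. The exclusion rule over the four serology results** (Section 3.2.2.5)

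| HCV antibody | HBsAg | Rule as written (both) | Rule with 'or' |
|---|---|---|---|
| + | + | excluded | excluded |
| − | + | **not excluded** | excluded |
| + | − | not excluded | excluded |
| − | − | not excluded | not excluded |

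The second row is the gap. Sections 3.2.5, 3.4.1.1, 3.4.1.4 and 3.4.7.2 call for hepatitis history or testing but attach no eligibility consequence, so nothing elsewhere closes it by serology.

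**Step 2. What the HBsAg monitoring does for the patient in the second row** (Sections 3.4.1.2, 3.4.1.4, 3.4.7.2)

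- *No hepatitis B antibody, or previously vaccinated.* The trigger is not met, so no HBsAg follow-up is required.
- *Antibody-positive and unvaccinated* (for example by core antibody, which is measured in everyone). HBsAg is repeated every 4 weeks, but it was positive at entry, so another positive result shows no change. This assumes a positive/negative assay; the documents describe no quantitative one.

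In neither case can the scheduled HBsAg test identify reactivation. In an HBsAg-negative patient with antibody, the same test works as intended.

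**Step 3. How many patients might be affected**

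Inputs:
- n = 60 planned patients (Section 3.1).
- p = proportion of otherwise eligible patients who are HBsAg-positive and HCV-antibody-negative. The documents do not give p; 0.1% to 2% is an assumption.

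Formulas: expected number = 60p; chance of at least one = 1 − (1 − p)^60.

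| Assumed p | Expected number, 60p | Chance of at least one |
|---|---|---|
| 0.1% | 60 × 0.001 = 0.06 | 1 − 0.999^60 = 5.8% |
| 0.5% | 60 × 0.005 = 0.30 | 1 − 0.995^60 = 26.0% |
| 1% | 60 × 0.01 = 0.60 | 1 − 0.99^60 = 45.3% |
| 2% | 60 × 0.02 = 1.20 | 1 − 0.98^60 = 70.2% |

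These are upper figures, since they suppose that the literal rule is followed and that no other safeguard stops enrolment. They give the chance that such a patient is enrolled, not the chance of reactivation, which is lower by a factor the documents do not allow one to estimate.

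**The case against.** The strongest reply is that the sentence can be read as a list of disqualifying results, each sufficient alone. The context favours that meaning: everyone is tested, the rule follows at once, and the monitoring presupposes HBsAg-negative entrants. Where the lipid criterion in 3.2.2.1 needs logical operators, it capitalises them; this sentence does not. On that view the monitoring problem is not a second defect, because it arises only under the less likely reading.

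The intended meaning is very probably 'either', and the monitoring problem does follow from the wording of the exclusion. But eligibility is checked against the criteria as written, by the Principal Investigator or a designee (Section 3.2.2), and an exclusion rule should not have to be inferred from a monitoring table.

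The second reply is that other safeguards apply:

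- **At entry:** review of all baseline results (3.2.2), liver-function limits (3.2.2.1), exclusion of active or uncontrolled severe infection, liver disease and significant medical illness (3.2.2.5), and treatment of existing infections and a detailed hepatitis history (3.2.5).
- **On treatment:** AST, ALT and bilirubin every 2 weeks for 2 months and then monthly (3.4.1.2), dose interruption at grade 3 and discontinuation at grade 4 for non-hematological toxicity (Table 3-1), at least weekly follow-up after interruption for a suspected drug effect (3.2.4), and monthly case discussion (3.4.5.2). Section 3.2.5.3 does not tie reactivation to HBsAg, so other evidence could also trigger removal.

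These measures lower the likelihood of harm, and an investigator could well use the infection criterion to keep such a patient out. None of them names HBsAg, however. A well carrier with normal liver tests may not be judged to meet the clinical exclusions. No section links a rise in liver enzymes to hepatitis B testing, and Table 3-1 allows a tolerable grade 2 non-hematological toxicity to continue at full dose.

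Two further points stand. The prevalence range has no source in the documents, so little weight should rest on its upper end. And the 'or' wording also excludes patients positive only for HCV antibody, which rests on presumed intent and not on a stated harm.

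**Conclusion.** The concern holds: the exclusion is wrong as written. On its literal wording it admits by serology an HBsAg-positive, HCV-antibody-negative patient, and the scheduled HBsAg test cannot show reactivation in that patient. The conclusion rests on the literal reading and on a positive/negative assay.

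The size is modest: probably no more than about one patient in 60 even at the top of the assumed range, with general safeguards reducing the risk further. It still merits correction because the sentence is an operative eligibility rule, the harm is one the protocol recognises as serious, and the remedy is nearly free. Confidence is medium, given the evident intent and the other safeguards.

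**What to change.** Reword the exclusion in Section 3.2.2.5 so that either result suffices and the antigen is named, for example: *A positive result for HCV antibody or for hepatitis B surface antigen (HBsAg), alone or together, makes a patient ineligible.*

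Leave the antibody-triggered HBsAg monitoring in 3.4.1.2, 3.4.1.4 and 3.4.7.2 as it stands. It will then apply only to HBsAg-negative patients, in whom it is informative.

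The cost is a one-sentence amendment. Both markers are already measured before enrolment, so no procedure is added. The downside is the possible loss of a few patients positive on a single marker, which is probably what the rule was meant to do.
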